10.6 Interim analysis and criteria for the premature termination of the trial

No interim analyses will be performed. See 7.10 for stopping criteria.

10.7 Participant population

The primary analyses for all analysis (primary, secondary, safety) will be done on an ITT basis, with patients included in the groups to which they were randomised, irrespective of whether they received their allocated treatment.

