8.4 Treatment storage and supply

8.4.1 Storage: Sambucol/placebo will be stored at ambient temperature, below 25°C there are no temperature monitoring requirements needed.

8.4.2 Shipment: Treatments will be supplied Free of Charge by Pharmacare (Europe) Limited.

8.4.3 Ordering and Re-Ordering: Initial shipment will be shipped to site following site activation. Further supplies – logistics as agreed between site and Pharmacare.

8.4.4 Receipt: Shipments will be received by Pharmacy Clinical Trial Staff and inspected for any damage or defects. In the event of product defect or damage contact [contact] and cc. [contact]

8.4.5 Accountability: Pharmacy will keep an inventory log for stock received. The Batch number will be recorded in the CRF of product issued to each participant. No other accountability records will be kept.

8.4.6 Dispensing: On confirmation of eligibility, e consent and randomisation will occur. Patients will be randomised to active or placebo liquid and a 14 day supply of study liquid dispensed The Research Nurse will write the Patient's Trial ID No. on the label and record the Batch number in the patient's record The liquid can either be collected by a family member or friend and dropped to the patient's doorstep – or the research team will drop to the doorstep so that everyone has a chance to take part. If a participant lives further away the liquid will be delivered to their home address by courier

8.4.7 Recall Procedure: In the event of a product defect participants will be telephoned and asked to stop taking the product and either to destroy as for household waste or to return any unused product

to site according to the seriousness of the defect. Further investigation will be by Pharmacare's Recall Procedure, as appropriate.

BERRY Protocol v 6.2 22.07.2021 IRAS 282732

8.4.8 Post-trial access to Sambucol Liquid: Various Sambucol® products are readily available to purchase from Health Food stores, Pharmacies and various on-line retailers. Sambucol will not be supplied to participants after the end of the trial.

Blinding: Active Sambucol and Placebo will be packaged and labelled as THE BERRY TRIAL LIQUID. The active and placebo packs will be differentiated by – Q and Z respectively appended to the Batch Number. Packs will be received and stored by unblinded Pharmacy Staff and personnel distributing treatments to participants will also be unblinded.

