8.11 Assessment of compliance with treatment

Participants will be asked to confirm their compliance during planned telephone interviews with research staff on days 3,7,10 and 14.

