9.2 Operational definitions for (S)AEs

BERRY Protocol v 6.2 22.07.2021 IRAS 282732

The following adverse events are known manifestations of COVID-19 related disease. They will not be recorded in the medical notes as (S)AEs as part of this COVID-19 intervention trial.

- Chills
- Loss of taste and/or smell
- Cough
- Bloody sputum
- Sore throat
- Nasal symptoms: blocked or runny nose
- Ear pain
- Wheezing
- Chest tightness
- Shortness of breath
- Muscle aches
- Joint pain /heaviness
- Fatigue
- Headache
- Confusion
- Loss of appetite
- Abdominal pain
- Nausea/vomiting
- Diarrhoea
- Sore, red, gritty eyes
- Skin rash / irritation
- Dry/Sore lips
- Mouth Ulcers
- High Temperature

Evaluation of adverse events

The Sponsor expects that adverse events (apart from expected AEs) are recorded in the medical notes from the point of Informed Consent regardless of whether a participant has yet received a medicinal product. Individual adverse events should be evaluated by the investigator. This includes the evaluation of its seriousness, and any relationship between the investigational medicinal product(s) and/or concomitant therapy and the adverse event (causality).

Assessment of seriousness

Seriousness is assessed against the criteria in section 9.1. This defines whether the event is an adverse event, serious adverse event or a serious adverse reaction

Assessment of causality

Definitely: A causal relationship is clinically/biologically certain. **This is therefore an Adverse Reaction**

Probable: A causal relationship is clinically / biologically highly plausible and there is a plausible time sequence between onset of the AE and administration of the investigational medicinal product and there is a reasonable response on withdrawal. **This is therefore an Adverse Reaction.**

Possible: A causal relationship is clinically / biologically plausible and there is a plausible time sequence between onset of the AE and administration of the investigational medicinal product. **This is therefore an Adverse Reaction.**

BERRY Protocol v 6.2 22.07.2021 IRAS 282732

Unlikely: A causal relation is improbable and another documented cause of the AE is most plausible. **This is therefore an Adverse Event.**

Unrelated: A causal relationship can be definitely excluded and another documented cause of the AE is most plausible. **This is therefore an Adverse Event.**

Unlikely and Unrelated causalities are considered NOT to be trial drug related

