9.3 Recording and reporting of SAEs, SARs AND SUSARs

All **SAEs** occurring from the time of start of trial treatment until 14 days post cessation of trial treatment must be recorded on the Trial data collection form and scanned and emailed to the Sponsor **within 24 hours** of the research staff becoming aware of the event. The original form will be copied and held by the Sponsor.

The Chief Investigator is responsible for ensuring that the assessment of all SAEs for relatedness and expectedness is completed and the onward notification of all SARs to the Sponsor immediately or not more than 24 hours of first notification. The sponsor has to keep detailed records of all SARs reported to them by the trial team.

All SAEs/SARs may be reported by the trial team to Pharmacare UK.

Adverse Reactions will be reported to the REC if they could:

- adversely affect the health of participants
- impact on the conduct of the trial
- alter the risk to benefit ratio of the trial
- alter the competent authority's authorisation to continue the trial in accordance with Directive 2001/20/EC

For each **SAEs** the following information will be collected:

- full details in medical terms and case description
- event duration (start and end dates, if applicable)
- action taken
- outcome
- seriousness criteria
- causality (i.e. relatedness to trial drug / investigation), in the opinion of the investigator
- whether the event would be considered anticipated.

Events will be followed up until the event has resolved or a final outcome has been reached."

BERRY Protocol v 6.2 22.07.2021 IRAS 282732

All SAEs assigned by the PI or delegate (or following central review) as both suspected to be related to treatment and unexpected will be classified as SUSARs and will be subject to expedited reporting to the REC. The sponsor will inform the REC and Manufacturer of SUSARs within the required expedited reporting timescales.”

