10.3 Statistical analysis plan

A full Statistical Analysis Plan (SAP) will be developed and agreed in advance of any data analysis.

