10.3.2 Primary outcome analysis

The primary outcome, VAS symptoms score at 10 days, will be analysed using Analysis of Covariance (ANCOVA). The scores at 10 days will be used as the outcome variable, with the symptom scores at baseline included as a covariate.

The primary analysis will be performed on an Intention to Treat (ITT) basis. Participants will be analysed in the arm to which they were randomised, irrespective of whether they received their allocated treatment.

If the population varies for the ITT analysis, a per protocol analysis will be performed, as a sensitivity analysis.

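### Section 10.7 analyses safety by randomised arm whatever was taken; a took-at-least-one-dose set grouped by product received would be a cheap improvement, though the bias is probably small

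*Combined protocol and SAP*

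**What the plan says.** Section 10.7 sets one rule for every analysis and names safety in it: "The primary analyses for all analysis (primary, secondary, safety) will be done on an ITT basis". The rest of that sentence keeps each person in the assigned arm even if the allocated liquid never reached them. The only other population is in section 10.3.2, where, if the ITT population varies, "a per protocol analysis will be performed, as a sensitivity analysis". That sentence concerns the primary outcome. Section 10.3 adds that "A full Statistical Analysis Plan (SAP) will be developed and agreed in advance of any data analysis"; that plan is not among the documents.

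The recording windows differ. Under section 9.2, adverse events outside the list of expected COVID-19 manifestations are noted "from the point of Informed Consent regardless of whether a participant has yet received a medicinal product". Under section 9.3, serious adverse events are recorded on the trial form when "occurring from the time of start of trial treatment until 14 days post cessation of trial treatment".

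On exposure, section 8.4.5 says "The Batch number will be recorded in the CRF of product issued to each participant" and that, beyond this and the pharmacy stock log, no accountability records are kept. Section 8.11 says "Participants will be asked to confirm their compliance during planned telephone interviews with research staff on days 3,7,10 and 14". The follow-up row of the section 7 table also has participants asked about missed doses.

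**The concern.** Analysing by randomised arm protects an efficacy comparison, where dilution works against the product. For harm, the same dilution works in the product's favour: people who took nothing cannot show an effect of the liquid, and they reduce the difference between arms.

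The design leaves room for both routes to dilution. Randomisation comes before supply, and the liquid reaches participants through a relative or friend, a doorstep drop or a courier (sections 7 and 8.4.6), so no first dose is observed. Active and placebo bottles carry the same trial label and differ only by a Q or Z after the batch number (section 8.4 and Appendix 1).

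Attribution also matters here. Section 7.5 names a new allergy to the food colouring as the likeliest reason to unblind, and section 8.1 lists colourants only for the placebo. If a participant randomised to Sambucol were issued placebo and reacted to the colouring, section 10.7 would count that reaction against Sambucol.

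**Working it through.** **Arm size.** Section 10.1 gives SD 20, difference 10, 5% significance and 90% power. A two-sided t-test calculation gives 85.03, rounded up to 86 per group (172), as stated. With 15% dropout, 86 / 0.85 = 101.2, rounded up to 102 per arm, or 204, as stated. These figures are not in dispute; 102 per arm is used below.

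**Assumed inputs.** The documents give no adverse-event risk, non-starter share or dispensing-error rate. The main illustration takes a risk of 20% among those who take active liquid and 10% among those on placebo.

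**Non-starters at background risk.** Let a share f of each arm take nothing and carry the 10% risk. By randomised arm:

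- active-arm risk = (1 - f) x 20% + f x 10%
- difference = (1 - f) x 10 points

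Power is for a two-sided 5% comparison of two proportions, first with 102 per arm as randomised, then with 102 x (1 - f) per arm among takers only.

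| f | Active risk by randomised arm | Difference (points) | Power, randomised arm | Power, takers only |
|---|---|---|---|---|
| 2% | 19.8% | 9.8 | 50.2% | 50.8% |
| 5% | 19.5% | 9.5 | 48.1% | 49.6% |
| 10% | 19.0% | 9.0 | 44.6% | 47.5% |
| 15% | 18.5% | 8.5 | 41.1% | 45.3% |

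With 15% v 5% instead, the difference again falls from 10 points to between 9.8 and 8.5. Power is 65.1% to 55.4% by randomised arm, against 65.6% to 59.4% among takers.

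**Non-starters with no recorded events.** For serious events a never-starter has no recording window under section 9.3 and adds only to the denominator. Both risks are then multiplied by (1 - f). With the same assumed risks and f = 10%, 20% v 10% becomes 18.0% v 9.0%. The difference shrinks to the same 9.0 points, and the ratio stays at 2.

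**Swapped supplies.** If e participants per arm receive the other arm's liquid, the difference is multiplied by (1 - 2e/102):

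- e = 1: 10 x (1 - 2/102) = 9.8 points
- e = 2: 10 x (1 - 4/102) = 9.6 points
- e = 5: 10 x (1 - 10/102) = 9.0 points

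**Against sampling error.** The 95% half-width for 20% v 10% with 102 per arm is 1.96 x sqrt((0.20 x 0.80 + 0.10 x 0.90) / 102) = 1.96 x sqrt(0.25 / 102) = 9.7 points. A shift of 0.5 to 1.0 point is about 5% to 10% of that.

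**The case against.** The strongest case against is that little is at stake.

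- Safety is neither an objective nor an endpoint in section 3, and section 10 describes no adverse-event table or test. A reader might infer that the trial sets out to confirm a clean safety record and that this rule helps it do so. The documents do not support that: the absence of known side effects is stated as background (sections 2, 2.1 and 8.3), not as an aim.
- Section 10.8 omits patients with missing data, and section 7.10 stops data collection at withdrawal. Never-starters who leave or give no follow-up may therefore drop out of the safety analysis anyway. This stands: dilution needs never-starters who stay in follow-up.
- Nothing in the documents shows that non-starting or mis-dispensing is common. Distributing staff are unblinded and the batch number is recorded, so a wrong bottle can be detected. A reader might infer that errors are expected; the documents show only that they are possible.
- Section 9.2 keeps nausea, vomiting, diarrhoea, abdominal pain and rash out of adverse-event recording. That could remove more safety signal than the dilution does. It is a separate matter and does not justify the population rule.
- Section 10.7 speaks of primary analyses, and a full SAP is promised, so a supplementary as-treated table is not excluded. But none is specified, and a SAP that made product received the main safety grouping would depart from a rule the protocol already states.

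These points limit the size. They do not remove the mismatch between the safety denominator and the serious-event window, or the misattribution after a wrong issue.

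**Conclusion.** The point holds as a cheap improvement. Section 10.7 commits safety to the randomised arm regardless of exposure, and no other section supplies a set based on what was taken. The direction of bias is towards no difference. Under assumed risks of 20% v 10%, 5-10% non-starters turn 10 points into 9.5-9.0, and one to five swapped supplies per arm turn it into 9.8-9.0. The power cost relative to analysing takers is 0.6 to 4.2 points for 2% to 15% non-starters. All of this rests on rates that the documents do not give, and on non-starters who remain in follow-up.

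A reader might conclude that the safety results would be seriously misleading. The figures do not support that: the shift is small beside a sampling half-width of 9.7 points. Nor is it right that everything needed is already recorded. The batch number shows what was issued; whether any was taken rests on self-report, and no first-dose date is listed.

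**What to change.** In section 10.7, limit ITT to the efficacy analyses. State that safety will be analysed in all participants who took at least one dose, grouped by product received, with the randomised-arm table as supplementary. Carry the same definition into the SAP.

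Take product received from the batch number issued (section 8.4.5), and exposure from the missed-dose question and compliance interviews (sections 7 and 8.11). Two additions make this workable:

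- have the day 3 contact confirm explicitly that a first dose was taken;
- count participants whose exposure is unknown, such as those lost before day 3, as exposed to the product issued.

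The cost is a short amendment to 10.7, one question at day 3 and one extra table. The downsides are a slightly smaller safety denominator and exposure that rests on self-report, because no bottle return or volume check is planned. The sample size does not change.

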10.8 Procedure(s) to account for missing or spurious data

Spurious data will be identified and checked with original source documentation. If found to still be spurious, based on clinical values may be excluded from the analysis. Any omissions will be noted and justified.

Patients with missing data for any given variable will be omitted from the analysis. No imputations of missing data will be performed.

10.9 Other statistical considerations

None noted

11 DATA MANAGEMENT

11.1 Data collection tools and source document identification

CRF

All data will be transferred into a Case Report Form (CRF) which will be labelled using a participant's unique trial ID. All trial data in the CRF must be extracted from and be consistent with, the relevant source documents. The CRFs must be completed, dated and signed by the investigator or designee in a timely manner. It remains the responsibility of the investigator for the timing, completeness, legibility and accuracy of the CRF pages. The CRF will be accessible to trial coordinators, data managers, the investigators, Clinical Trial Monitors, Auditors and Inspectors as required.

The institution will keep records of all participating patients (sufficient information to link records e.g., CRFs, hospital records and samples), all original signed informed consent forms and copies of the CRF pages.

All CRF pages must be clear, legible and completed in ink. Any errors should be crossed with a single stroke so that the original entry can still be seen. Corrections should be inserted and the change dated and initialled by the investigator or designee. If it is not clear why the change has been made, an explanation should be written next to the change. Typing correction fluid must not be used.

The CRF contains the validated VAS scoring system and will be used to record patient wellness.

To enable peer review, monitoring, audit and/or inspection records of all participating participants (sufficient information to link records e.g., CRFs, hospital records), all original signed informed consent forms and copies of the CRF pages.

Source data may include but is not limited to:

- Signed informed consent forms
- Patient medical records (electronic or paper)
- Clinical research forms/folders

11.2 Data handling and record keeping - Data Protection & Participant Confidentiality

Paper CRFs will be kept in a securely locked room with restricted access. Data will be uploaded to the REDCap database for analysis. Access is password -protected. All patient data will be collected and stored in accordance with the Data Protection Act 1998 and the General Data Protection Regulation.

11.3 Access to Data

Direct access will be granted to authorised representatives from the Sponsor, host institution and the regulatory authorities to permit trial-related monitoring, audits and inspections- in line with participant consent.

11.4 Archiving

- archiving will be authorised by the Sponsor following submission of the end of trial report
- if the sponsor and trial site are the same, archiving will occur as per standard procedure.
- the location and duration of record retention for:

BERRY Protocol v 6.2 22.07.2021 IRAS 282732

- essential documents 5 years
- the trial database 10 years
- destruction of essential documents will require authorisation from the Sponsor

- If a study participant becomes an inpatient, their medical records are source data and must be retained for the same retention period as the essential documents.
- If a study participant becomes an inpatient, their medical records should be clearly marked that the patient has taken part in a clinical trial and they should not be destroyed (this should apply to all volumes of patient's medical records)
- The label must clearly state the retention period
- The hospital notes of patients will not be archived with the TSF, as they may still be important for any on-going medical care. Only certified copies of the patient notes that are directly relevant to the study can be archived with the TSF, if necessary.

12 MONITORING, AUDIT & INSPECTION

A Trial Monitoring Plan will be developed and agreed by the Trial Management Group (TMG), TSC and CI based on the trial risk assessment. A detailed monitoring plan will be generated detailing the frequency and scope of the monitoring for the trial. This will be dependent on a documented risk assessment of the trial. Throughout the course of the trial, the risk assessment will be reviewed and the monitoring frequency adjusted as necessary.

The investigator will make all trial documentation and related records available should an Inspection occur. Should a monitoring visit or audit be requested, the investigator will make the trial documentation and source data available to the Sponsor's representative. All participant data will be handled and treated confidentially.

13 ETHICAL AND REGULATORY CONSIDERATIONS

13.1 Research Ethics Committee (REC) review& reports

- Before the start of the trial, approval will be sought from a REC for the trial protocol, informed consent forms and other relevant documents e.g. advertisements and GP information letters. Substantial amendments that require review by REC will not be implemented until the REC grants a favourable opinion for the trial.
- All correspondence with the REC will be retained in the Trial Master File/Investigator Site File
- An annual progress report (APR) will be submitted to the REC within 30 days of the anniversary date on which the favourable opinion was given, and annually until the trial is declared ended

- It is the Chief Investigator's responsibility to produce the annual reports as required.
- The Chief Investigator will notify the REC of the end of the trial
- If the trial is ended prematurely, the Chief Investigator will notify the REC, including the reasons for the premature termination
- Within one year after the end of the trial, the Chief Investigator will submit a final report with the results, including any publications/abstracts, to the REC

13.2 Peer review

No external Peer Review has been undertaken.

13.3 Public and Patient Involvement

Patients have not been involved in the formulation of the study due to constraints of time. Dissemination of results will be publicised for patients to review.

13.4 Regulatory Compliance

- The trial will not commence until Favourable REC and HRA approval is received.
- For any amendment to the study, the Chief Investigator or designee, in agreement with the sponsor will submit information to the appropriate body in order for them to issue approval for the amendment. The Chief Investigator or designee will work with sites (R&D departments at NHS sites as well as the study delivery team) so they can put the necessary arrangements in place to implement the amendment to confirm their support for the study as amended.

13.5 Protocol compliance

Prospective, planned deviations or waivers to the protocol are not allowed under the UK regulations on Clinical Trials and must not be used.

Protocol deviations, non-compliances, or breaches will be adequately documented on the relevant forms and reported to the Chief Investigator and Sponsor immediately.

Deviations from the protocol which are found to occur repeatedly will not be accepted and will require immediate action and could potentially be classified as a serious breach.

